 - Stratified block randomization will be used to ensure that the number of participants is equally distributed among the study groups and stratified by surgery level (major, minor). The allocation sequence will be generated with block size of 4 using computer software. Randomization will be implemented with the REDCap Randomization module. Randomization schedule can only be accessed by a research personnel not directly involved in patient care. The patient's 6-week postoperative visit will be scheduled according to her assigned group.
- Study instruments:
 - Study instruments will be administered at the preoperative visit and the 6-week postoperative visit. The questionnaires for this study include the Patient Preparedness Questionnaire (PPQ), the Patient Satisfaction Questionnaire-18 (PSQ-18), and modified patient and provider preference questionnaires entitled, Patient Postoperative Visit Questionnaire and Provider Postoperative Visit Preference Questionnaire.
 - The PPQ will be administered during the preoperative visit to assess patient knowledge and preparedness for surgery, which has been demonstrated in other studies to impact postoperative satisfaction, perceived complications, and drug utilization.¹⁰⁻¹¹ The PPQ is a 11-item questionnaire scored on a six-point Likert scale and has responses ranging from 1 (strongly agree) to 6 (strongly disagree).⁹ The questionnaire for this study will utilize the same six-point scale with a reversed scoring system, ranging from 1 (strongly disagree) to 6 (strongly agree). Although there are currently no validated measures to assess surgical preparedness in urogynecology, the PPQ has been used in several studies assessing surgical preparedness in women undergoing pelvic organ prolapse and/or stress urinary incontinence.^{8,12} These studies utilized the same cutoff score for question 11 (i.e., an answer of "strongly agree" to the question "overall, I feel prepared for my upcoming surgery") to define meeting criteria for preoperative preparedness.
 - The PSQ-18 will be administered after the 6-week postoperative virtual or in-office visit to assess patient satisfaction with their postoperative visit. The PSQ-18 is a

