- Emergency department or urgent care visits during the next six weeks following the scheduled 6-week postoperative visit (Y/N); if Y,
 - Total number of ED/urgent care visits (No. of occurrences)
 - Date of ED visit #1 (MM/DD/YYYY)
 - Reason/s for ED visit
 - Outcome of ED visit (discharge, readmission, reoperation, other-specify)
 - Date of ED visit #2 (MM/DD/YYYY)
 - Reason/s for ED visit
 - Outcome of ED visit (discharge, readmission, reoperation, other-specify)
- Hospital readmissions during the next six weeks following the scheduled 6-week postoperative visit (Y/N); if Y,
 - Total number of hospital readmissions
 - Date of readmission #1
 - Reason/s for readmission
 - Outcome of readmission (discharge, reoperation, other-specify)
 - Hospital length of stay (no. of days)
- Adverse events during the next six weeks following the scheduled 6-week postoperative visit (Y/N); if Y, specify (urinary tract infection, neurologic injury, hemorrhage/hematoma, blood transfusion, wound infection and cellulitis, seroma, abscess, pyelonephritis, sepsis, vaginal fistula, vaginal dehiscence, deep venous thrombosis, pneumonia, drainage of abscess, delayed gastrointestinal injury, delayed genitourinary injury, ileus, small bowel obstruction, pulmonary embolism, myocardial infarction, cerebrovascular accident and stroke, death, mesh complication, readmission, reoperation)
- Power Analysis and Sample Size Calculation
 - The primary outcome of this study is to compare patient satisfaction between patients scheduled for office versus virtual six-week postoperative visits.
 - A priori sample size calculation determined that 100 participants (50 per group) would allow for 80% power to assess a noninferiority margin of 5 points on the

total PSQ-18, with a SD of 10 and significance level of 0.05. A minimum important difference has not been reported for the PSQ-18; however, previous studies using this tool demonstrated SD for total PSQ-18 score ranging between 2.6 and 11.8 and used a 5-point interval for the noninferiority margin.^{6,13} To account for an anticipated attrition rate of approximately 5%, we aimed to enroll a total of 106 participants (53 per group).

- **Statistical Analysis**

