- Patient satisfaction (PSQ-18) total scores, as well scores in each of the 7 PSQ-18 domains, will be treated as continuous data and checked for normality. Healthcare utilization will be analyzed individually (number of phone calls, number of outpatient visits, number of emergency department or urgent care visits, number of hospital readmissions), as well as a composite of all encounter types. Adverse events will be analyzed independently but also as a composite utilizing the Clavien-Dindo Grading System for surgical complications. Attitudes toward office/virtual visits will be analyzed by comparing proportions of patients and providers who prefer a virtual visit, prefer an office visit, or have no preference.
- All analyses will be conducted using an intention-to-treat principle. Baseline demographic and clinical characteristics will be summarized using descriptive statistics. Normally-distributed continuous measures will be summarized using mean and standard deviation (SD), whereas those showing departure from normality will be summarized using median and interquartile range (IQR). Categorical measures will be summarized using number of participants and percentage. The primary end-point analysis will be designed to test whether patient satisfaction with a virtual postoperative visit is noninferior to an in-person postoperative visit, as determined by the total PSQ-18 at the scheduled postoperative visit. Noninferiority would be shown if the lower limit of the two-sided 95% confidence interval for the between-group mean difference in the primary endpoint (i.e., the difference between the mean PSQ-18 total score in the virtual group minus the mean PSQ-18 total score in the in-office group) is more than -5 points. Similar analyses will be performed for each secondary outcome. The noninferiority margin is defined as 5 points for the PSQ-18 total score and 0.5 points for the PSQ-18 domain scores, 10% absolute for composite healthcare resource utilization, and 25% absolute for composite adverse events. Planned exploratory subgroup analyses of patient satisfaction, healthcare resource utilization and adverse events based on surgery level will be additionally performed.
- All statistical analyses will be performed using JMP Pro version 17.0 software (SAS Institute, Cary, NC).
- Data will be managed in REDCap. Statistical support will be provided by the Cleveland Clinic Quantitative Health Sciences.

E. PRIVACY AND CONFIDENTIALITY

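### The stated 80% power for the primary endpoint fits a one-sided 5% test; under the plan's own two-sided 95% CI rule, 50 per group give about 70%.

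*Combined protocol and SAP*

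**What the plan says.** In section D, Power Analysis and Sample Size Calculation, the plan states that "100 participants (50 per group) would allow for 80% power to assess a noninferiority margin of 5 points" on the PSQ-18 total score, "with a SD of 10 and significance level of 0.05". The sidedness of the 0.05 is not given, and neither is the true difference assumed under the alternative. The SD is put in context by the remark that "previous studies using this tool demonstrated SD for total PSQ-18 score ranging between 2.6 and 11.8". The target is then raised to 106 enrolled (53 per group) for attrition of about 5%.

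In section D, Statistical Analysis, the success criterion is: "Noninferiority would be shown if the lower limit of the two-sided 95% confidence interval for the between-group mean difference" lies above -5 points, where the difference is virtual minus in-office. The same margin is repeated there: "The noninferiority margin is defined as 5 points for the PSQ-18 total score". Neither part mentions a one-sided 5% test or a 90% confidence interval, and nor does any other part of the document.

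**The concern.** A noninferiority claim made on the lower limit of a two-sided 95% interval uses only the 2.5% in that tail. It is a one-sided test at 0.025. A sample size computed with 0.05 in one tail belongs to a different, more lenient rule, equivalent to a two-sided 90% interval. If 50 per group was derived that way, the 80% does not describe the analysis that will be done.

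Two things are at stake. First, a noninferiority trial that misses its margin is inconclusive, and a reader who believes the power was 80% will misjudge such a miss. Second, while the two parts disagree, someone could later cite the 0.05 in the sample-size paragraph to justify a 90% interval. That would double the one-sided error from 2.5% to 5%.

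**Working it through.** **Inputs**

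- Margin M = 5 points (both parts of section D).
- SD = 10 (sample-size paragraph).
- 50 evaluable per group, 1:1 allocation (sample-size paragraph; Randomization in section C).
- Stated power 80%, so z = 0.842.
- True difference 0. This is an assumption, because the plan gives none.
- Alpha: one-sided 0.05 (z = 1.645) or one-sided 0.025 (z = 1.960). The second is what the stated decision rule implies.

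**Step 1: reproduce the plan's figure**

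n per group = 2 × (z_alpha + z_power)² × (SD/M)²

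- One-sided 0.05: 2 × (1.645 + 0.842)² × (10/5)² = 49.5, which rounds up to **50**. This matches the plan.
- One-sided 0.025: 2 × (1.960 + 0.842)² × (10/5)² = 62.8, which rounds up to **63**. This does not match.

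With the t distribution the two figures are 51 and 64. The attrition step also reproduces: 100/0.95 = 105.3, so 106. The arithmetic is sound for a one-sided 5% test.

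**Step 2: power at 50 per group under each rule**

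Standard error of the difference = 10 × √(2/50) = 2.0, so M/SE = 2.5.

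| Rule | Normal approximation | Noncentral t |
|---|---|---|
| One-sided 0.05 | Φ(2.5 − 1.645) = 0.804 | 0.799 |
| One-sided 0.025 (the plan's rule) | Φ(2.5 − 1.960) = 0.705 | 0.697 |

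**Step 3: does the attrition allowance close the gap?**

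If all 53 per group were evaluable, SE = 10 × √(2/53) = 1.943 and M/SE = 2.574. Power is Φ(2.574 − 1.960) = 0.730 (t: 0.722), still short of 80%.

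**Step 4: sensitivity at 50 per group under the 95% CI rule**

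| Assumption changed | Power (normal approximation) |
|---|---|
| SD 8 | 0.88 |
| SD 9 | 0.79 |
| SD 10 (the plan's value) | 0.71 |
| SD 11.8 (top of the quoted range) | 0.56 |
| SD 10, true difference +1 (favours virtual) | 0.85 |
| SD 10, true difference −1 | 0.52 |

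The break-even SD for 80% power is 5 / [(1.960 + 0.842) × √(2/50)] = 8.9 (t: 8.8). At SD 10, the true advantage for virtual visits that restores 80% is (1.960 + 0.842) × 2.0 − 5 = 0.6 points.

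**The case against.** The strongest reply is that the 70% is conditional. The plan states neither the sidedness of its 0.05 nor a true difference, so the one-sided 5% basis is inferred from the match with 50 per group. A true advantage of about 0.6 points for virtual visits would bring the 95% CI rule back to roughly 80%. The SD may also be smaller than 10. Most of the quoted range of 2.6 to 11.8 lies below the break-even of 8.8 to 8.9, and at the midpoint of 7.2 power is about 0.93. The low figure at SD 11.8 is only partly due to alpha, since a one-sided 5% test would have just 0.68 power there.

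These remarks are correct and should condition how the figure is quoted. They do not rescue the 80%. The plan itself chose SD 10 and states no favourable difference; its primary hypothesis is noninferiority only. Nor does it help to read the 0.05 as two-sided. The alpha would then agree with the decision rule, but 50 per group would no longer follow from it, because that reading needs 63.

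A second reply is that the decision rule is clear, prespecified and the stricter of the two, so a positive result would remain valid. That also stands. The damage is to the stated power and to the reading of a negative result, not to type I error. A further objection is that restating the power leaves the trial no better powered. That is true, but the restatement makes the claim accurate at almost no cost.

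**Conclusion.** The concern holds. The stated sample size and the stated decision rule belong to different tests. With margin 5, SD 10, 50 evaluable per group and an assumed true difference of 0, power under the two-sided 95% CI rule is about 70% (0.705 normal, 0.697 t), against the 80% claimed. The risk of an inconclusive result when the two visit types are truly equal is about 30% instead of 20%. That the original calculation used one-sided 0.05 is an inference, but a strong one: it reproduces the plan's number and the 0.025 version does not. This must be corrected, because it concerns the primary endpoint and the stated justification for enrolling 106 patients.

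**What to change.** Keep the two-sided 95% CI rule and correct the sample-size paragraph to match it. Suggested wording: *With 50 evaluable participants per group, a noninferiority margin of 5 points, an SD of 10, an assumed true difference of 0 and a one-sided alpha of 0.025 (lower limit of the two-sided 95% confidence interval), power is about 70%.*

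This costs one sentence and a less favourable power figure. It needs no extra patients and no change to the analysis, and it rules out a later move to a 90% interval on the strength of the unqualified 0.05.

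If the sponsor wants to keep 80% under the same rule, the trial needs 63 per group, or 126 evaluable. At 5% attrition that is 126/0.95 = 132.6, so 133, or 134 enrolled with equal groups. With the t-based 64 per group it is 64/0.95 = 67.4, so 68 per group, or 136 enrolled.

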will inquire about any concerns the patient has regarding recovery, followed by any unanticipated healthcare encounters at outside facilities. These outside healthcare encounters will be documented by the provider in their Epic note to facilitate data collection by the study investigators. The provider will review key aspects of postoperative care (bowel function, urinary function, presence of vaginal bleeding, dietary status, and ambulatory status), postoperative instructions and precautions, findings and procedures done during surgery, and pathology results (if applicable). The provider will then visually examine surgical sites and document their findings in their Epic note. The provider will inquire about any additional questions from the patient and perform additional evaluation/treatments per standard of care. The PSQ-18 and the Patient Postoperative Visit questionnaire will be administered after this visit. The patient may be contacted for up to two times by a study investigator via phone, text or email within 48 to 72 hours after the visit regarding completion of study questionnaires using a script.

- **Provider Recruitment and Study Procedures**
 - Surgeons and advanced practice providers will be educated about the study during the Urogynecology Section Research Meeting as part of the provider recruitment process.
 - After the six-week virtual or in-office visit, the provider will fill out the Provider Information Sheet and the Provider Postoperative Visit Preference Questionnaire. The provider will complete the questionnaire at the end of the visit. If this is not feasible, the provider will be sent a text reminder for up to two times to their Cleveland Clinic issued phone number within 48 to 72 hours after the visit.

	Preoperative Visit	Day of Surgery	Postoperative Visit (6 weeks)	End of study follow-up (12 weeks after surgery)
Questionnaire: PPQ	X			
Questionnaire: PSQ-18			X	
Questionnaire: Patient Postoperative Visit			X	
Questionnaire: Provider Postoperative Visit Preference			X	
Data collection: Demographic and baseline clinical characteristics	X			
Data collection: Perioperative characteristics		X		
Data collection: Postoperative healthcare resource utilization, adverse events			X	X

D. DATA ANALYSIS PLAN

- Data Collection

- A) Demographic data will include the following:
 - Date of preoperative visit (MM/DD/YYYY)
 - Route of preoperative visit with surgeon (in-office/virtual)
 - MRN
 - Age (years)
 - Race
 - Ethnicity

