 - Marital status
 - Distance from home to clinic (miles)
 - Vaginal parity
 - Menopausal state
 - Current tobacco use (Y/N)
 - BMI (kg/m²)
 - Comorbid conditions (MI, CHF, peripheral vascular disease, cerebrovascular disease, dementia, chronic pulmonary disease, connective tissue disease, ulcer disease, mild liver disease, diabetes, diabetes with end organ damage, hemiplegia, moderate or severe renal disease, any tumor without metastasis, leukemia, lymphoma, moderate or severe liver disease, metastatic solid tumor, AIDS)
 - Charlson Comorbidity Index (CCI) score
 - *Calculation for CCI: diabetes with complications, hemiplegia/paraplegia, renal disease, and malignancies, age 60-69 are assigned a score of 2; age 70-79 moderate/severe liver disease is assigned a score of 3; metastatic solid tumour and AIDS/HIV are assigned a score of 6; the remaining comorbidities are assigned a score of 1*
 - Prior prolapse surgery (Y/N; if Y, specify)
 - Prior anti-incontinence surgery (Y/N; if Y, specify)
 - Preoperative prolapse overall stage based on POP-Q exam (0, I, II, III, IV)
 - Preoperative POP-Q points (Aa, Ba, C, GH, PB, TVL, Ap, Bp, D)
 - Preference for text or email reminder communication
 - Preferred mobile phone number or email address
- B) Perioperative data will include the following:
 - Date of surgery (MM/DD/YYYY)
 - Location of OR facility
 - Surgery level (Minor, Major)
 - Surgery type
 - Concomitant procedures
 - Operative time (minutes)
 - Estimated blood loss (ml)
 - Intraoperative complications (bladder injury, ureteral kinking, bowel injury, vascular injury, EBL ≥300 ml, transfusion, conversion to open procedure, other-specify)
 - Hospital length of stay (no. of hours if <24 hours; no. of days if >24 hours)
 - If patient was admitted, was the admission planned (Y/N)

- If N, specify reason for postoperative admission
- Voiding trial results (Pass/Fail)
 - If Fail, select outcome: foley catheter reinserted, patient taught intermittent self-catheterization
- Postoperative prescriptions at discharge (name, dosing, quantity)

○ C) Six-week postoperative data will include the following:

- Date of postoperative visit (MM/DD/YYYY)
- Number of days postop at 6-week visit
- Route of postoperative visit (in-office, virtual)
 - If virtual, was an in-office visit recommended for further evaluation (Y/N); reason for office evaluation (specify)

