 - If virtual, did the patient require assistance with using video conference technology prior to their scheduled appointment (Y/N)
 - If virtual, were there any technological difficulties during the visit (Y/N)
- Did the patient cross-over to the other group at any point before the 6-week visit (Y/N)?
- Provider conducting postoperative visit (APRN, MD, other-specify)
- Abdominal exam performed (Y/N); if Y, list findings (normal, abnormal-specify)
- Pelvic/vaginal exam performed (Y/N); if Y, list findings (normal, abnormal-specify)
- Patient-initiated phone call to surgeon's office prior to 6-week postoperative visit (Y/N); if Y,
 - Total number of phone calls (No. of occurrences)
 - Date of phone call #1 (MM/DD/YYYY)
 - Reason/s for phone call #1
 - Outcome of phone call (counseling/reassurance, prescription sent, new order placed, new office/virtual appointment scheduled, advised to go to ED/urgent care, provider placed follow-up call to patient the next day, other-specify)
 - Date of phone call #2 (MM/DD/YYYY)
 - Reason/s for phone call #2
 - Outcome of phone call
 - Date of phone call #3 (MM/DD/YYYY)
 - Reason/s for phone call #3
 - Outcome of phone call
- Unanticipated outpatient (office/virtual) visits to surgeon's office prior to 6-week postoperative visit (Y/N); if Y,
 - Total number of outpatient visits including office voiding trials (No. of occurrences)
 - Total number of voiding trial visits (No. of occurrences)
 - Date of outpatient visit #1 (MM/DD/YYYY)
 - Reason/s for outpatient visit
 - Outcome of outpatient visit (counseling/reassurance, prescription sent, new order placed, new office/virtual appointment scheduled, advised to go to ED/urgent care, hospital/direct admission, reoperation, provider/patient to place follow-up call, other-specify)

- Date of outpatient visit #2 (MM/DD/YYYY)
 - Reason/s for outpatient visit
 - Outcome of outpatient visit
 - Date of outpatient visit #3 (MM/DD/YYYY)
 - Reason/s for outpatient visit
 - Outcome of outpatient visit
- Emergency department or urgent care visits prior to 6-week postoperative visit (Y/N); if Y,
 - Total number of ED/urgent care visits (No. of occurrences)
 - Date of ED visit #1 (MM/DD/YYYY)
 - Reason/s for ED visit
 - Outcome of ED visit (discharge, readmission, reoperation, other-specify)
 - Date of ED visit #2 (MM/DD/YYYY)
 - Reason/s for ED visit
 - Outcome of ED visit (discharge, readmission, reoperation, other-specify)

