- Hospital readmissions prior to 6-week postoperative visit (Y/N); if Y,
 - Total number of hospital readmissions
 - Date of readmission #1
 - Reason/s for readmission
 - Outcome of readmission (discharge, reoperation, other-specify)
 - Hospital length of stay (no. of days)
- Adverse events prior to postoperative visit (Y/N); if Y, specify (urinary tract infection, neurologic injury, hemorrhage/hematoma, blood transfusion, wound infection and cellulitis, seroma, abscess, pyelonephritis, sepsis, vaginal fistula, vaginal dehiscence, deep venous thrombosis, pneumonia, drainage of abscess, delayed gastrointestinal injury, delayed genitourinary injury, ileus, small bowel obstruction, pulmonary embolism, myocardial infarction, cerebrovascular accident and stroke, death, mesh complication, readmission, reoperation)
- D) Twelve-week postoperative data will include the following:
 - End of follow-up (i.e., date marking 6 weeks after the patient's scheduled 6-week postoperative visit) (MM/DD/YYYY)
 - Number of days postop at date above
 - Patient-initiated phone call to surgeon's office during the next six weeks following the scheduled 6-week postoperative visit (Y/N); if Y,
 - Total number of phone calls (No. of occurrences)
 - Date of phone call #1 (MM/DD/YYYY)
 - Reason/s for phone call #1
 - Outcome of phone call (counseling/reassurance, prescription sent, new order placed, new office/virtual appointment scheduled, advised to go to ED/urgent care, provider placed follow-up call to patient the next day, other-specify)
 - Date of phone call #2 (MM/DD/YYYY)
 - Reason/s for phone call #2
 - Outcome of phone call

- Unanticipated outpatient (office/virtual) visits to surgeon's office during the next six weeks following the scheduled 6-week postoperative visit (Y/N); if Y,
 - Total number of outpatient visits including office voiding trials (No. of occurrences)
 - Total number of voiding trial visits (No. of occurrences)
 - Date of outpatient visit #1 (MM/DD/YYYY)
 - Reason/s for outpatient visit
 - Outcome of outpatient visit (counseling/reassurance, prescription sent, new order placed, new office/virtual appointment scheduled, advised to go to ED/urgent care, hospital/direct admission, reoperation, provider/patient to place follow-up call, other-specify)
 - Date of outpatient visit #2 (MM/DD/YYYY)
 - Reason/s for outpatient visit
 - Outcome of outpatient visit

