Protection of each subject's personal health information will be a priority in this study. One master Excel file containing subject personal information including name and medical record number will be kept in a password-protected file, on a designated protected research drive on a password-protected computer in a locked office at the Cleveland Clinic. In that file, each subject will be assigned a subject identification number that will be used for the purposes of data collection in order to de-identify subjects. All paper forms used for data collection will be kept in a research cabinet dedicated to this project which will be locked at all times, in a

locked office at the Cleveland Clinic. All forms will contain de-identified information; identification numbers will correspond to the subjects listed in the master Excel file. All study data will be transferred and managed electronically using REDCap. Each subject will be entered into REDCap using the assigned identification number from the master Excel file.

F. DATA/SAMPLE SHARING

Not applicable

G. ADVERSE EVENTS AND DATA MONITORING

Any adverse event or unanticipated events will be reported as soon as feasible to the IRB using IRB WebKit. Examples of adverse events include inability to attend the postoperative visit due to technological issues (If the visit cannot be completed due to technological issues, the provider will ensure that the appointment is rescheduled to another time that is convenient and acceptable to the patient). All events will be recorded and kept in a research binder assigned to this study in a locked office. Monthly reviews during the study period will be done by all involved study staff members to ensure that events are not occurring, and if they are, that they are being handled and reported properly. The study will be terminated if patients in the intervention arm have decreased satisfaction of 20% compared to the control arm. This will be assessed monthly at the reviews mentioned above.

H. STUDY TIMELINE

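### No masking is stated for whoever classifies the 6-to-12-week secondary outcomes, and the data set shows the visit route, so that person would probably know the arm

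*Combined protocol and SAP*

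**What the plan says.** Section B gives noninferiority hypotheses for utilization and adverse events, and Outcome Measures (section C) places both between the scheduled postoperative visit and week 12. Statistical Analysis (section D) sets their margins at 10% and 25% absolute. On grading it says "Adverse events will be analyzed independently but also as a composite utilizing the Clavien-Dindo Grading System for surgical complications".

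The twelve-week part of Data Collection has fields for patient-initiated calls and for "Unanticipated outpatient (office/virtual) visits to surgeon's office during the next six weeks following the scheduled 6-week postoperative visit (Y/N". Outcome Measures calls the visits unscheduled; the form calls them unanticipated. Neither term is defined, nor is patient-initiated.

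The six-week part of the same data set holds "Route of postoperative visit (in-office, virtual", several fields completed only for virtual visits, and "Did the patient cross-over to the other group at any point before the 6-week visit (Y/N".

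The only wording close to masking is in the Randomization text: "Randomization schedule can only be accessed by a research personnel not directly involved in patient care". It limits access to the allocation schedule. The identification numbers in section E protect privacy and do not hide the arm. The document says nothing, in either direction, about masking of abstractors, graders or analysts.

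**The concern.** Patients and providers cannot be masked to the type of visit, but the person who classifies events can be. If that person knows the arm, borderline items may be counted differently in the two arms. In a noninferiority comparison, under-counting in the virtual arm pushes towards the conclusion the study hopes to reach.

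One ambiguity is built in unevenly. The form asks, for virtual visits only, whether an in-office visit was recommended for further evaluation. The plan does not say whether the resulting visit counts as unanticipated. Not counting it would favour noninferiority.

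At stake are two secondary comparisons with stated margins, not the primary result.

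**Working it through.** **Would the classifier know the arm?** Setting the sections side by side:

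- Statistical Analysis requires a graded composite but names no grader.
- Data Collection puts visit route, virtual-only fields and cross-over status in the same participant's data as the outcome fields. Recording cross-over requires knowing the assigned group.
- The Randomization text restricts the schedule, not outcome assessment.

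Someone working through the participant's data would therefore see the arm unless a step removed it, and no such step is described. This is an inference from silence and from the fields.

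**The number per arm.** The plan plans for 50 per group, with margin 5, SD 10, significance level 0.05 and 80% power. This reproduces with a one-sided 0.05 level: n = 2 × (1.645 + 0.842)² × (10/5)² ≈ 49.5, so 50. Allowing for 5% attrition, 50/0.95 = 52.6, so 53 per group and 106 in total. The 50 is used below only as a denominator.

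**Effect of one reclassified patient.** Assume that each composite is the proportion of patients with any qualifying event. The percentage margins suggest this, but the plan does not say so, and it also lists numbers of encounters.

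- One patient: 1/50 = 2 points, which is 2/10 = 20% of the utilization margin and 2/25 = 8% of the adverse-event margin.
- Five patients, all moved the same way in one arm: 5/50 = 10 points, which is 100% of the utilization margin and 40% of the adverse-event margin.

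Two points is a maximum. A patient changes status only if every qualifying event is discounted, or if a single newly counted one is the only one.

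**Sensitivity of the noninferiority decision.** The documents give no event rates, so these are assumptions: control proportion p from 10% to 50%, true virtual proportion p + m (exactly at the margin m), and a fraction u of virtual-arm patients with an event wrongly not counted. The observed virtual proportion is q = (p + m)(1 − u), the observed difference is d = q − p, and s = √[q(1 − q)/50 + p(1 − p)/50]. The chance of falsely declaring noninferiority is Φ((m − d)/s − 1.96).

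Example for utilization, with p = 0.10, m = 0.10 and u = 0.20: q = 0.16, d = 0.06, s = 0.067, and Φ(0.04/0.067 − 1.96) = 8.6%.

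| Not counted in virtual arm | Utilization (m = 0.10) | Adverse events (m = 0.25) |
|---|---|---|
| 0% | 2.5% | 2.5% |
| 10% | 4.7% to 8.7% | 6.5% to 11.8% |
| 20% | 8.6% to 22.4% | 14.8% to 32.8% |

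For utilization, the 20% row means 0.20 × 0.20 × 50 = 2 patients at p = 10% and 0.20 × 0.60 × 50 = 6 patients at p = 50%. The table shows how sensitive the decision is. It does not estimate a bias, because nothing in the documents indicates what u would be.

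**The case against.** The strongest reply is that the plan is silent on masking rather than unmasked by design, and that little judgement is needed. Adverse events are recorded against a list of 25 named items. Calls and visits carry dates, reasons and outcomes. Whether a visit was unscheduled can largely be read from the appointment record. Much of this stands, and it confines the point to borderline visits and calls, the less clear-cut adverse events, and the grade.

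Four stronger readings are tempting, and the documents do not support them:

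- *The plan has arm-aware investigators grade the events.* It names no grader. Knowledge of the arm is probable but inferred.
- *The visit provider's note is the source of the endpoint data.* The plan does say "These outside healthcare encounters will be documented by the provider in their Epic note to facilitate data collection by the study investigators", but this concerns encounters reported at the 6-week visit, before the endpoint window opens. The twelve-week part names neither a source nor an abstractor.
- *Endpoints are graded at the monthly staff reviews.* Section G says "Monthly reviews during the study period will be done by all involved study staff members to ensure that events are not occurring", and its purpose is handling and reporting of events. Nothing there assigns grades or classifies endpoints. The reviews matter only because staff may come to know cases and arms.
- *The damage could never be repaired.* Dates, reasons and outcomes of recorded encounters are kept, so a reader without the arm could reclassify them later.

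It is also fair to object that removing the visit route could take away information needed to apply a definition. That is why the definitions must come first.

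**Conclusion.** The point holds as a low-severity improvement. As written, the plan leaves the judgement items in two secondary noninferiority comparisons open to classification by someone who probably knows the arm. The patient-reported PSQ-18 primary outcome is not touched, and emergency visits, readmission, reoperation and death leave little room for judgement.

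The size and direction of any bias cannot be estimated from the documents. The bound of 2 points per reclassified patient rests on 50 per arm and a patient-level proportion. The false-declaration rates rest further on assumed event rates and assumed one-directional under-counting. A reader might infer that the secondary results would be biased; the documents support only that the plan does not guard against it.

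**What to change.** First, write the definitions. Use one term for *unanticipated* and *unscheduled*, state whether an office visit recommended at the scheduled visit counts, with the same rule in both arms, and define *patient-initiated*. State whether each composite is a proportion of patients or a count of encounters.

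Then prepare a listing of encounters and events for the 6-to-12-week window without arm, scheduled-visit route or visit provider. Flag on it whatever the definitions require, in a form that does not show the arm where possible. An existing team member who did not conduct that patient's visit, and who as far as possible has not discussed the case at the monthly reviews, assigns unanticipated visit, patient-initiated call, adverse event yes/no and Clavien-Dindo grade. Lock these fields before merging the arm.

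This needs no extra patients, visits or assessor, only a modest amount of listing work. Masking will be incomplete, because some narratives reveal the visit type and staff may recall cases. Report that as a limitation. If the listing is not adopted, the plan should at least name the grader, give the definitions and state that classification was not masked.
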